## INTRO/Background:

There are millions of births each year with 32% of women undergoing cesarean sections (C-sections), which results in skin scarring. Repeat C-sections increased by 178% from 1979 to 2010. Given the frequency of C-sections, it is important to achieve a desirable cosmetic outcome.

Pathological scars can result in functional impairment, disfigurement, a psychological burden, itch, and even chronic pain. All scars are at risk to develop into pathological scars, such as hypertrophic or keloid scars. These types of scars can induce the need for long-term rehabilitation, revision surgery or other invasive therapies.

To reduce complicated scar formation, some have proposed the use of incisional negative pressure wound therapy (iNPWT). Although recent studies have shown certain limitations of the use of iNPWT, the general consensus remains that iNPWT helps to reduce surgical site complications such as infections and dehiscence in non-contaminated surgery.

Furthermore, several studies have reported beneficial effects of iNPWT on scar development. The underlying mechanism is hypothesized to be the reduction of lateral wound tension. Excessive lateral tension is generally considered to be a factor in pathological scar formation, and reduction of incisional tension has previously been shown to result in more favorable scar outcomes. Studies into the biomechanical properties of iNPWT demonstrated lateral tension reduction of the epidermis, fat, and muscle, supporting the hypothesis that negative pressure reduces sheer tension. In a recent systematic review by Zwanenburg et al., the conclusion was that there is a moderate level of evidence for clinically positive effects of iNPWT on scar outcomes in non-contaminated surgery.

The PICO 7 dressing consists of a negative pressure wound therapy pump (NPWT) connected to an absorbent gentle adhesive dressing that is applied to a wound. When the pump is activated, it acts by pulling excess fluid from the wound. The dressing absorbs this fluid and helps to prevent bacteria from entering the wound.

Figure 1: PICO-7 NPWT Device

Studies have been done using patient satisfaction scales to compare cosmetic outcomes of skin closure with tissue adhesive or staples in repeat cesarean section as well as cosmetic outcomes of cesarean section scar with subcuticular vs intradermal buried suture but none have been done to compare PICO

vs standard abdominal dressing. The effect of negative pressure wound therapy on patients scar outcomes and quality has been studied for gender affirming chest masculinization surgery.

Thus, this study aims to compare the aesthetic appearance by using The Patient and Observer Scar Assessment Scale (POSAS) scar assessment scale following closed incision negative pressure therapy with a PICO 7 dressing to the standard abdominal dressing in women undergoing repeat cesarean sections.

## **Methods:**

### **Study design and participants:**

This study was a single site, randomized controlled trial at a teaching hospital in Indiana for patients undergoing a repeat cesarean delivery. Participants were randomized using 1:1 block randomization to placement of a PICO-7 dressing or a standard abdominal dressing (generally telfa, ABD gauze dressing, tegaderm +/- steristrips) at the time of cesarean. The standard abdominal dressing was removed approximately on postoperative day (POD) 1-2 and the PICO-7 dressing was removed approximately on POD 3-4 (prior to discharge) or at POD7 in the office. If the patient with a PICO dressing remained inpatient for longer than 7 postoperative days, the PICO dressing was removed prior to POD7, in accordance with device instructions. The patients were given routine postoperative incision care instructions during their inpatient stay, which includes education per OB-GYN residents, attending staff, and nursing.

Participants in both groups were sent electronic POSAS surveys at the two, four and six week postop window with primary outcome being aesthetic appearance (cosmesis) at six weeks. Observers (healthcare providers) were asked to complete a POSAS survey at the postpartum visit (~4-6 weeks postoperative) to rate scar quality. Participants were offered compensation with a \$25 Amazon gift card for participants who completed the requested follow up in the study. These were provided by Smith and Nephew.

The eligibility criteria is listed here as follows:

### **Eligibility Criteria**

- 1.1 Inclusion Criteria-Patient**
  - Scheduled or non-labor repeat cesarean delivery
  - One or more prior cesarean section(s) with prior pfannenstiel incision scar
  - Gestational age > 23 weeks
  - Age 18 and older
- 1.2 Exclusion Criteria-Patient**
  - Patients with malignancy in the wound bed or margins of the wound
  - Non-enteric and unexplored fistulas
  - Necrotic tissue with eschar present
  - Exposed arteries, veins, nerves or organs
  - Exposed anastomotic sites
  - Cellulitis or evidence of active infection
  - Known allergy to adhesive tape
  - Patient unwilling to follow-up
  - Contraindication to NPWT
    - o Bleeding disorder
    - o Therapeutic anticoagulation
    - o Allergy to any component of the dressing

- o Prior irradiated skin
- Warnings to NPWT
  - o The PICO 7 pump contains a Magnet that can cause other medical devices in close proximity to fail, leading to serious harm including death. The PICO 7 pump must be positioned at least 4 inches (10 cm) away from other medical devices that could be affected by magnetic interference. This applies to both patients and caregivers. These include but are not limited to:
    - § Implantable cardioverter-defibrillator (ICD)
    - § Pacemakers
    - § Insulin pumps
    - § Shunt valves
    - § Neurostimulators
    - § Cochlear implants

[figure not shown]

Figure 2: Study Design

### **Data Collection:**

The Patient Scar Assessment Scale (POSAS) rates 6 variables: scar-related pain, itching, color, stiffness, thickness, and irregularity. Each parameter is scored on a 1- to 10-point ordinal scale, with 1 indicating that the scar is comparable with normal skin and 10 reflecting the worst imaginable scar. The sum of the 6 individual parameters ranges from 6 (normal skin) to 60 (worst scar).

The POSAS patient survey was e-mailed to participants at the two, four, and six-week time intervals and data collected and stored via REDCap. Participants were sent each survey up to 3 times until a response was logged. If they did not respond electronically, each patient was then called up to 3 times. The POSAS observer survey was completed and collected at the time of the patient interview (routinely a postpartum visit). The observer (MD/DO/NP seeing the patient) was also asked to upload a picture of the cesarean section scar into the EMR. Baseline patient characteristics including maternal age, BMI, and number of prior cesarean sections were abstracted from the EMR.

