### Discussion/Conclusions:

In this study, we assessed the influence of incisional negative pressure wound therapy on scar development and patient satisfaction with their cosmetic outcome. We performed a pilot randomized controlled trial to test two equivalent incisions. Generally, the results of this study showed a potential small difference in favor of iNPWT in patient-reported outcome measures with a lower score on the POSAS score at 6 weeks and a lower observer score and overall score of the scar at 4-6 weeks postpartum. These outcomes could not be analyzed for any sort of statistically significant values due to the low recruitment and even lower patient follow up and response rate despite attempting to reach patients by both several emails and phone calls.

Strengths of this study include an even 1:1 block randomization at a single site (Eskenazi Hospital) with a robust Labor and Delivery unit with a diverse patient population. Limitations of this study include a small sample size and low patient follow up response rate, which yielded data that was unable to be analyzed for statistical significance. In statistical considerations in study design, we expected a 20% drop-out by 6 weeks. However in our study, we had a 35% drop out rate (no response in any of the three surveys), and only 12.5% of patients filled out all 3 weeks of the surveys. 42% of patients did not attend their scheduled postpartum visit at the 4-6 week mark. Many of the other

studies that were performed using NPWT compared to standard abdominal dressing were done to evaluate the benefits on wound healing and preventing surgical site infections. The study that was performed to evaluate potential patient cosmesis benefits when using NPWT compared to standard dressing was a gender affirming mastectomy, which was ultimately an elective and cosmetic surgery which could have contributed to having higher patient follow up rates. It is possible that patient follow up and participation could have been lower than expected as a cesarean section is a medically necessary and not a cosmetic surgery, and the participants of this study were all recruited at a county hospital that serves a largely low income and resource population. Lastly, the participants of this study were all taking care of newborn children as well. All of these can cause difficulty with follow up and are also potential barriers to care, as seen by the overall low follow up for medical care at the post partum visit.

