Sponsor: Smith & Nephew

Negative Pressure Wound Therapy-PICO: Cosmesis in Repeat Cesarean Section

Device: PICO-7 Negative Pressure Wound Pump

NCT # 05266053

Document Date: 04/25/24

[name], Assistant Professor

Department of Obstetrics & Gynecology

[name]

[name]

Statistical Analysis:

We plan to enroll approximately 100 women with a previous C-section, which will be randomized 1:1 to either the standard dressing or PICO 7 dressing. The primary outcome will be the patient component of the Patient and Observer Scar Assessment Scale (POSAS) assessed at 2 weeks, 4 weeks, and 6 weeks following C-section. The primary time point of interest will be at 6 weeks since we expect the most improvement will be seen at the later time point. If approximately 20% drop-out by 6 weeks, then with $N = 80$ (40 per group), we will have 80% power to detect a .7 SD difference in mean scar assessment at 6 weeks between the two-groups using a two-sample t-test with equal variance and type I error set at 0.05 which provides conservative power compared to our linear mixed model. Based on a small RCT pilot study for C-section scars which used this instrument (Ekin et al., 2018), the effect sizes for the Patient, Observer, and Total POSAS were $ES = 1.18, 1.03$, and 1.15 , respectively. Also, the pooled SD was 7.2 for the Patient version, thus assuming our population will have a similar SD in this measure; we will be able to detect approximately a 5-point change (0.7×7.2) in Patient POSAS. Thus, we should have adequate power to detect meaningful improvements in scar assessment.

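### No in-person completion of the primary patient POSAS is described at the 4-6 week visit, which about 14 of 24 women attended; the number of week-6 scores this cost cannot be determined

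*Protocol*

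**What the plan says.** The SAP states: "The primary outcome will be the patient component of the Patient and Observer Scar Assessment Scale (POSAS"), and adds that "The primary time point of interest will be at 6 weeks".

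The Protocol's Data Collection section gives two routes for that form. The first is electronic: "The POSAS patient survey was e-mailed to participants at the two, four, and six-week time intervals", and "Participants were sent each survey up to 3 times until a response was logged". The second is the telephone: "If they did not respond electronically, each patient was then called up to 3 times".

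The visit is described separately and only for the clinician's half of the instrument. Study design and participants says: "Observers (healthcare providers) were asked to complete a POSAS survey at the postpartum visit (~4-6 weeks postoperative) to rate scar quality". Data Collection says: "The POSAS observer survey was completed and collected at the time of the patient interview (routinely a postpartum visit"), and adds that the observer was asked to upload a photograph of the scar. Neither section mentions the patient form at that visit.

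On attendance, the Discussion reports: "42% of patients did not attend their scheduled postpartum visit at the 4-6 week mark".

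**The concern.** Staff holding one half of the POSAS see the woman at about the time the primary measurement is due, yet the half that carries the primary outcome is described as collected only at a distance. A woman who answers neither the e-mails nor the calls, but comes to the visit, would give no primary score under the procedure as written.

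This matters because the report names low response, together with low recruitment, as the reason it could not analyse its primary outcome. The documents also call for a further study with better follow-up, so the collection procedure may well be reused.

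**Working it through.** **Inputs**

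- Enrolled: 24 (Protocol, Statistical Analysis).
- Missed the 4-6 week visit: 42% (Discussion/Conclusions).
- Week-6 patient scores: 4 standard + 8 PICO = 12 (Table 2).
- Week-6 responders according to the text: 15 (Statistical Analysis; Patient demographics also gives 15 completing the primary outcome measures).
- Observer scores: 4 standard + 1 PICO = 5 (table of observer scores).
- Planned: about 100 enrolled, 20% drop-out, 0.7 SD, type I error 0.05 (Statistical Considerations; SAP). Sidedness is not stated; I take it as two-sided.

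**Step 1: reproduce the attendance figure.** 10/24 = 41.7%, which rounds to 42%. The neighbouring counts do not fit: 9/24 = 37.5% and 11/24 = 45.8%. So 10 missed the visit and A = 24 - 10 = 14 attended, taking all 24 enrolled women as the denominator.

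**Step 2: attenders without a week-6 score.** With R week-6 responders and no cross-tabulation, the number is bounded by max(0, A - R) and min(A, 24 - R).

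| Source of R | R | Minimum | Maximum |
|---|---|---|---|
| Table 2 | 12 | 14 - 12 = 2 | min(14, 12) = 12 |
| Text | 15 | max(0, -1) = 0 | min(14, 9) = 9 |

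Some loss among attenders is therefore certain under Table 2 and only possible under the text.

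**Step 3: how much a form at the visit might add.** If attendance and response were independent (an assumption), the attenders without a score would number 14 x 12/24 = 7.0 with R = 12, or 14 x 9/24 = 5.25 with R = 15. Recovering all of them would also need every woman to complete the form and every visit to fall close enough to week 6. The observer form, which was tied to this visit, gives a caution: 5/14 = 36% of attenders, if all five scores were taken there. Using that rate purely as an illustration, R = 12 becomes 12 + 7 x 5/14 = 14.5. This still counts every visit as week 6, although visits ran from about week 4.

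**Step 4: effect on power.** For 0.7 SD by a two-sided t-test, the Table 2 split of 4 and 8 gives about 18%. All 24 women scored, at 12 per group, gives about 37%. At the planned size of 100, completion matters more: 50% completion (25 per group) gives about 68%, against about 87% at the planned 40 per group.

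**The case against.** A reader might infer that the patient form was never given at the visit and that primary data were lost from women who were in the room. The documents support neither as fact. In-person completion is not described, but nothing excludes it, and the study-design and follow-up figures are not available in the text. The Discussion's account of attempts to reach women names only e-mails and calls, which makes the inference reasonable but not proven. Nor is ignoring e-mail enough to be lost, because telephone calls follow; a woman has to be missed by both routes.

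A reader might also take 12 + 7 = 19 of 24 as the expected yield. That figure uses the smaller of two conflicting counts and assumes independence, full completion and every visit inside the week-6 window. The Discussion attributes poor survey follow-up and missed visits to the same barriers (newborn care, limited resources). That points to overlap between non-responders and non-attenders, and so to a smaller gain.

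There is some reason to favour Table 2's 12. It is the only tabulation of the week-6 scores, and the stated 35% with no response to any survey lies between 8/24 = 33.3% and 9/24 = 37.5%. That leaves 15 or 16 women who answered at least one survey, so the text's 15 may be that count instead. This is suggestive only, and the conflict remains.

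Finally, it is fair to say that this gap did not sink the trial. Recruitment of 24 against about 100 would have left it underpowered with perfect follow-up.

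**Conclusion.** The point holds as a gap in the described procedure and a missed opportunity, not as a demonstrated loss. Between 0 and 12 of about 14 attenders lack a week-6 patient score: 2 to 12 by Table 2, 0 to 9 by the text. The documents do not allow the number, or the gain from collecting at the visit, to be fixed.

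The attendance figure rests on 42% being a share of all 24 women. Any gain depends further on the overlap between attendance and response, on completion at the visit, and on how many visits fall near week 6; none of these is reported. This is a worthwhile low-cost improvement for a repeat of the study. It would not have let this trial answer its question.

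**What to change.** Add to the Data Collection section that any woman attending the postpartum visit with an outstanding survey completes the patient POSAS herself, on paper or in REDCap, before the observer rates the scar. Record the date and the mode of completion.

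Define the week-6 window in advance. Count a visit form as the week-6 score only if it falls inside that window. Otherwise use it as week-4 data in the linear mixed model and still send the week-6 survey, so that an early visit does not displace the primary measurement.

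In the current report, reconcile the 15 week-6 responders in the text with the 12 scores in Table 2, and cross-tabulate visit attendance against week-6 response by group.

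The cost is one form and a few minutes at a visit that already takes place. The downside is mixed modes of completion and some scores taken before 6 weeks; a sensitivity analysis by mode and date should check whether either affects the comparison.

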### **Study outcomes:**

The primary study outcome was to compare aesthetic appearance and patient satisfaction at 6 weeks postoperative of a repeat C-section in NPWT-PICO dressing vs. standard abdominal dressing. The primary time point of interest was at 6 weeks as we expected the most improvement to be seen at that later time point.

The secondary objective was to compare incision healing complications up to 42 days postoperatively between the standard dressing group vs. the PICO NPWT group.

### **Statistical Considerations**

We planned to enroll approximately 100 women with a previous C-section. If approximately 20% drop-out by 6 weeks, then with  $N = 80$  (40 per group), we will have 80% power to detect a .7 SD difference in mean scar assessment at 6 weeks between the two-groups using a two-sample t-test with equal variance and type I error set at 0.05 which provides conservative power compared to our linear mixed model. Based on a small RCT pilot study for C-section scars which used this instrument (Ekin et al., 2018), the effect sizes for the Patient, Observer, and Total POSAS were  $ES = 1.18, 1.03$ , and  $1.15$ , respectively. Also, the pooled SD was 7.2 for the Patient version, thus assuming our population will have a similar SD in this measure; we will be able to detect approximately a 5-point change ( $0.7 \times 7.2$ ) in Patient POSAS. Thus, we should have adequate power to detect meaningful improvements in scar assessment.

### **Statistical Analysis:**

Characteristics of the study population were summarized using descriptive statistics. 24 patients were recruited and enrolled in the study. Out of these 24, only 3 patients that responded to all three (2-, 4- and 6- week) POSAS surveys. 15 patients responded to the 6 week assessment survey, which was the primary outcome of this study. For this reason, statistical analysis that would provide a statistically significant value was unable to be performed.

[figure not shown]

Figure 3: Enrollment and follow up

Results:

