**Patient demographics:**

In total, 24 patients were recruited in this study. Follow-up moments were between August 2022 and March 2023. Inclusion and surgery took place between July 2023 and January of 2023. A total of 15 participants completed the primary study outcomes measures (on scar quality and patient-reported outcomes) and were included for analysis. The patient demographics are presented in Table 1. The median age of the participants was 29.8 years (range 25–34.5) in the standard dressing group and 34.6 in the PICO-7 group (range 27–42). The average prior cesarean sections were 1.4 (range 1–3) in the standard dressing group and 1.7 (range 1–3) in the PICO-7 group. Only one of the patients declared to have experienced any problematic scarring previous to surgery (e.g., hypertrophy and/or keloid). Most of the included patients were Caucasian (87.5%).

Table 1: Descriptive Statistics

Variable	Standard dressing (N = 5)	PICO (N = 10)
Age, Mean (SD)	29.8 (4.7)	34.6 (7.5)
BMI, Mean (SD)	37.2 (11.9)	34.0 (5.1)
Number of Prior C-sections, Mean (SD)	1.4 (0.9)	1.7 (1.1)

Language		
English	4 (100%)	5 (50%)
Spanish	0	5 (50%)
Missing	1	
Ethnicity		
Non-Hispanic or Latino	5 (100%)	6 (60%)
Hispanic or Latino	0	4 (40%)
Race		
Black/African American	4 (80%)	5 (50%)
White	1 (20%)	1 (10%)
Unknown/not reported	0	4 (40%)

The Patient Scar Assessment Scale (POSAS) rates 6 variables: scar-related pain, itching, color, stiffness, thickness, and irregularity. Each parameter is scored on a 1- to 10-point ordinal scale, with 1 indicating that the scar is comparable with normal skin and 10 reflecting the worst imaginable scar, as seen in Figure 4 and Figure 5. The sum of the 6 individual parameters ranges from 6 (normal skin) to 60 (worst scar).

At week 2, the average patient score was 33 in the standard dressing group versus 19 in the PICO-7 group. At week 4, the average patient score was 24.5 in the standard dressing group versus 25 in the PICO-7 group. At week 6, the average patient score was 26.5 in the standard dressing group versus 13.0 in the PICO-7 group. The observer score was measured between 4-6 weeks at the patients postpartum visit. The average observer score was 19 in the standard dressing group versus the 16 in the PICO-7 group.

Table 2: Comparison of patient POSOS scores between the groups

Variable	Standard dressing	PICO
POSAS score Week 2, Median (Q1-Q2)	33.0 (17-49) [N = 2]	19.0 (16-32) [N = 5]

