POSAS score Week 4, Median (Q1-Q2)	24.5 (15-34) [N = 2]	25.0 (6-27) [N = 5]
POSAS score Week 6, Median (Q1-Q2)	26.5 (16-36.5) [N = 4]	13.0 (10-16.5) [N = 8]

Table 3: Comparison of observer POSOS scores between the groups

Variable	Standard dressing	PICO
Observer score, Median (Q1-Q2)	19.0 (11.5-39) [N = 4]	16 [N = 1]
Overall opinion of scar, Median (Q1-Q2)	7.0 (4-10) [N = 2]	2 [N = 1]

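### The week-6 patient POSAS comparison is left without an estimate or interval because few patients responded, yet the Discussion calls the difference small; low numbers limit precision but do not prevent estimation

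*Protocol*

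**What the plan says.** The SAP makes the patient component of the POSAS the primary outcome and states: "The primary time point of interest will be at 6 weeks". The Protocol agrees on week 6 under Study design and participants and under Study outcomes. The power text, the same in both documents, uses a two-sample t-test with equal variance, "which provides conservative power compared to our linear mixed model". The model's terms are given nowhere.

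Under Statistical Analysis, the Protocol reports 24 enrolled, 3 who answered all three surveys and 15 who answered at week 6, and concludes that "statistical analysis that would provide a statistically significant value was unable to be performed". Under Patient demographics it repeats: "A total of 15 participants completed the primary study outcomes measures".

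The results text then reads: "At week 6, the average patient score was 26.5 in the standard dressing group versus 13.0 in the PICO-7 group". Table 2 shows that these are medians. The standard-arm cell is "26.5 (16-36.5) [N = 4" (closing bracket omitted here); the PICO cell is 13.0 (10-16.5) with N = 8. No between-group difference, interval or p-value is given anywhere.

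The Discussion says that, generally, "the results of this study showed a potential small difference in favor of iNPWT", with lower patient and observer scores. Its final paragraph repeats that the score was lower with PICO. The Abstract's Conclusion, the Statistical Analysis section and the Discussion all say that the comparison could not be tested or evaluated.

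**The concern.** Two things do not fit together. First, the reason for omitting inference is that significance could not be expected. That is not a reason to omit an estimate: few patients make an interval wide, and the width is what the reader needs to see. Nor do only 3 complete responders rule out a mixed model, which uses partial responders too.

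Second, with no estimate reported, the Discussion still attaches a size and a direction to the result. Its hedged 'small' does not match the table. A reader may take 'small' at face value, or may read 13.5 points as a mean effect because the text calls the medians averages. Nothing printed shows how little the data say about either. The same sentence also leans on the observer score, which rests on 4 versus 1 patients, and on the overall opinion, which rests on 2 versus 1 (Protocol, observer-score table).

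The number of patients behind the primary result is also unclear: 15 in the text, 12 in Table 2.

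**Working it through.** **1. The plan's own figures.** The target is 0.7 × 7.2 = 5.04 points, as stated. Enrolment is 80 / (1 − 0.2) = 100, as stated. For 40 per arm, taking the test as two-sided, normal-approximation power is Φ(0.7 × √(40/2) − 1.96) = Φ(1.17) = 88% (87% with the t distribution). The stated 80% is conservative and does not affect this point.

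**2. The observed gap.** 26.5 − 13.0 = 13.5 points, and 13.5 / 5.04 = 2.7 times the target.

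**3. Is 4 versus 8 analysable?** There are C(12,4) = 495 ways to split 12 scores into 4 and 8, so the smallest two-sided exact rank-sum p is 2/495 = 0.004. Neither estimation nor testing is ruled out.

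**4. What Table 2 allows.** Assumptions:
- 12 is the right count.
- The bracket headed 'Q1-Q2' means Q1 to Q3, since its upper value lies above the median.
- Scores are integers from 6 to 60.
- Quartiles average adjacent ordered values. Linear interpolation is ruled out by the week-2 standard row (N = 2, median 33, Q1 17): the lower score a would satisfy 0.5a + 16.5 = 17, so a = 1, which is below the scale minimum.

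Standard arm, ordered scores: x1 + x2 = 2 × 16 = 32 and x3 + x4 = 2 × 36.5 = 73. The mean is (32 + 73)/4 = 26.25 in every matching data set.

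PICO arm: x2 + x3 = 20, x4 + x5 = 26 and x6 + x7 = 33, together 79. The smallest score lies in 6-10 and the largest in 17-60. The mean therefore runs from (79 + 6 + 17)/8 = 12.75 to (79 + 10 + 60)/8 = 18.625.

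Mean difference, standard minus PICO: 26.25 − 18.625 = 7.6 to 26.25 − 12.75 = 13.5.

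All 10 standard and 4,931 PICO data sets that match the table were combined and three 95% intervals computed for each pair:
- Equal-variance t: d ± 2.228 × s × √(1/4 + 1/8), with s the pooled SD on 10 degrees of freedom.
- Welch: d ± t × √(v1/4 + v2/8), with v1 and v2 the standard and PICO variances.
- Exact rank-based: the 5th and 28th of the 32 ordered pairwise differences (coverage 95.2%).

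| Method | Lower limit | Upper limit | Width |
|---|---|---|---|
| Equal-variance t | −15.3 to 3.6 | 22.5 to 31.5 | 19 to 47 |
| Welch | −16.9 to −4.8 | 26.8 to 39.1 | 35 to 51 |
| Exact rank-based | −14 to 2 | 24 to 33 | 22 to 47 |

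The scale is 60 − 6 = 54 points long.

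Two matching data sets show how much depends on the method and on unprinted scores:
- *Standard 15, 17, 36, 37; PICO 6, 10, 10, 13, 13, 16, 17, 17.* d = 13.5, v1 = 140.92, v2 = 15.36, s = √((3 × 140.92 + 7 × 15.36)/10) = 7.28. Equal-variance t: 13.5 ± 2.228 × 7.28 × 0.612 = 3.6 to 23.4. Welch: 13.5 ± 3.01 × 6.10 = −4.8 to 31.8. Rank-based: 0 to 26.
- *Standard 6, 26, 27, 46; PICO 10, 10, 10, 13, 13, 13, 20, 60.* d = 7.6, s = 16.83. Equal-variance t: −15.3 to 30.6. Welch: −16.9 to 32.1. Rank-based: −14 to 33.

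**5. The count.** Table 2 has 4 + 8 = 12 week-6 scores, so 24 − 12 = 12 enrolled patients have none. The text says 15.

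**The case against.** The documents do not hide the weakness. The Abstract concludes that the study cannot evaluate the dressing, Table 2 prints N = 4 and N = 8 beside the medians, and the sentence after the criticised one says that the outcomes could not be analysed for significance. The wording is hedged, and a lower PICO score is a correct description of the observed medians. Clearly labelled descriptive reporting would also be defensible for a trial that enrolled 24 of about 100. All of this stands and limits the harm. It does not rescue the stated reason, which treats low numbers as a bar to estimation, or the word 'small', which is a judgement of size rather than a description.

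Stronger readings are tempting but unsupported:
- *Three week-6 scores were left out of Table 2.* The Discussion says "we had a 35% drop out rate (no response in any of the three surveys" (closing bracket omitted here). With 15 responders to any survey that rate would be (24 − 15)/24 = 37.5%, near the stated 35%, so 15 may be an any-survey count. The documents do not settle it.
- *The interval would include zero*, or *the 13.5 points show a large benefit*. Neither follows. The first data set above excludes zero with one method and not with the others, and 13.5 is a difference of medians from 12 patients.
- *The planned mixed model could simply have been run.* Its terms are unspecified, and the number of patients with repeated scores is not given.

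**Conclusion.** The point holds as a reporting and analysis gap in the primary outcome. Low response explains imprecision, not the absence of a between-group estimate and interval. The warning is present; the numerical uncertainty is not, and 'small' is unsupported beside a 13.5-point gap in medians. On the assumptions in step 4 of the working, the data are too few to judge size and, depending on the method, direction. If the week-6 count is really 15, three scores are absent from Table 2 and the ranges do not apply, but the estimate is still missing. The ranges illustrate imprecision and do not replace an analysis of patient-level data. Even a correct interval would not cover non-response or the lack of blinding.

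**What to change.** 1. Reconcile 15 with 12 from the survey database, and correct either the text (Statistical Analysis, Patient demographics) or Table 2.
2. Replace the Statistical Analysis sentence with: *Because few patients responded, estimates are imprecise; the week-6 between-group difference is reported with 95% confidence intervals.* In the results text, call these figures medians.
3. From patient-level data, report the week-6 difference with all three intervals together: equal-variance t (the stated power basis), Welch and exact rank-based. Label them post hoc. Showing all three prevents a choice of method after the result is seen. Add the mixed model only if it can be fitted.
4. State per arm how many enrolled patients have no week-6 score, and that the intervals do not cover non-response or lack of blinding.
5. In the Discussion, replace the claim of a small difference with a statement that the observed median was lower with PICO but the estimate is too imprecise to judge size or, depending on the interval, direction. Deleting only 'small' would read as more favourable to PICO. Give the observer numbers (4 versus 1; overall opinion 2 versus 1), and add the same qualifier to the final paragraph, in line with the Abstract's Conclusion.

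The cost is a few hours on existing data plus text edits. The downside is wide intervals and an analysis that must be disclosed as post hoc.
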